99 100 The study will consist of an economic evaluation alongside a cluster randomized controlled trial using 101 a 1 year follow-up. Effectiveness and cost-effectiveness of the tailored lifestyle intervention will be 102 evaluated in comparison with usual care. Before the persons with SMI are recruited, participating 103 FACT-teams will be randomly allocated to the tailored lifestyle intervention or usual care. 104 105 The study will be carried out in two parts. At first, half of the centres will start with the trial and about 106 6 months later, the other centres will start. The tailored lifestyle intervention lasts 12 months in total. 107 Including inclusion of participants, analysis and reporting phase, the total duration of the SMILE study 108 will be 48 months. 109 110 JUSTIFICATION STUDY DESIGN 111 Randomization will be performed at the level of the FACT teams. All persons with SMI receive the 112 same treatment within a cluster (FACT team). Major reason for this randomization procedure is to 113 avoid contamination of the treatment within the same FACT team. It is not possible to blind persons 114 with SMI and FACT team professionals to the allocated intervention due to the nature of the tailored 115 lifestyle program. However, the pragmatic design of the study enhances the external validity. Staff 116 from FACT teams in the usual care control group will not be trained to perform the tailored lifestyle 117 intervention until after the end of the trial. That way, FACT team members cannot unintentionally 118 apply aspects of the intervention to their usual care for the SMI patients. 119 120 121 122

98

STUDY DESIGN

129	Population (base)
130	SMI is defined according to the consensus paper by Delespaul and the consensus group SMI [16].
131	Persons have SMI when: - there is a psychiatric disorder which requires long-term treatment and care
132	(symptomatic not in remission); - and which is accompanied by severe impairment in social
133	interaction and / or social functioning (non-functional remission); - the severe impairment is the cause
134	and effect of a mental illness; - it is structurally c.q. a long time, at least several years; - coordinated
135	care from professionals in care networks is indicated to realize the treatment plan. The consensus
136	group also stated that SMI cannot be limited to certain psychiatric diagnoses. The most prevalent
137	psychiatric disorders in the group of patients with SMI are: schizophrenia and related psychotic

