138	disorders, mood disorders (including bipolar disorder), severe personality disorders and addition
139	disorders.
140	Adults (≥18 years) with SMI in care by Flexible Assertive Community Treatment (FACT) teams in the
141	Netherlands will be included. The study aims to recruit 260 patients in total (for more information
142	regarding the power calculation, see chapter 3.4). The prevalence of persons with SMI is 1.3%
143	(n=216.000) of the total population and 1.6% (n=160.000) of the population of \geq 18 and 65 years in
144	the Netherlands in 2013. About 75% is cared for by the GGZ (Mental Health and Addiction Care
145	institutes) or other providers [16]. In the Netherlands there are approximately 250 certified FACT-
146	teams.
147	
148	Inclusion criteria
149	In order to be eligible to participate in this study, a subject must meet all of the following criteria:
150	• patient with SMI
151	• age ≥18
152	• body mass index ≥27
153	 willing to and able to sign informed consent (mentally competent)
154	
155	Exclusion criteria
156	A potential subject who meets any of the following criteria will be excluded from participation in this
157	study:
158	• Contra-indications (to be assessed by the treating physician/psychiatrist) for participation due
159	to acute psychiatric crisis or somatic diseases (e.g. bariatric surgery, cancer, heart attack or
160	stroke)
161	Subjects with a cognitive impairment sufficient to interfere with their ability to provide

informed consent, complete study questionnaires, or participate in a group intervention.

127 128

162

STUDY POPULATION

163 Women who are pregnant, breastfeeding, or planning a pregnancy during the course of the 164 study 165 Subjects not able to communicate in the Dutch language 166 167 Sample size calculation 168 This trial is powered to detect a mean difference of 4 kilograms in weight reduction after 1 year 169 between the intervention and usual care group [10, 17]. This difference is based on the outcomes of 170 multiple clinical trials including STRIDE, ACHIEVE and PREMIER [10, 14, 15, 17, 18]. using a 171 power of 0.80, an alpha of 0.05 and an SD of 10 two groups of 100 patients are needed to detect a 172 difference of 4 kilograms. Assuming an ICC of 0.01 for clustering of persons with SMI within a 173 FACT-team, and a dropout rate of 20% [10, 14, 15], the aim is to recruit 260 patients in total. 174 175 176 177

TREATMENT OF SUBJECTS

Investigational treatment

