333	Randomisation, blinding and treatment allocation
334	RANDOMISATION
335	Before persons with SMI are recruited, participating FACT-teams will be randomly allocated to serve
336	as intervention condition (where the tailored lifestyle intervention will be implemented) or control
337	FACT-teams (where care as usual will be given). Patients will be allocated to either one of the
338	treatment conditions, based on the FACT-teams that treated them.

339	Randomisation will be stratified by centers. This is done to ensure the comparability between FACT
340	teams and therefore reduce bias. The randomization results will be communicated to the participating
341	FACT-teams by the researchers.
342	Randomisation will be performed by a statistician blinded to the characteristics of the FACT-teams
343	using a computer generated list of random numbers.
344	BLINDING
345	Blinding of patients and FACT-team members is not possible due to the nature of the intervention.
346	The statistician and health economist will be blinded for the allocation of the intervention by keeping
347	the information of the allocation of the intervention in a separate data file.
348	The assessors of measurements will also not be blinded, because if they are employed by the FACT-
349	team they will know whether the fact team provides the lifestyle intervention or not.
350	
351	Study procedures
352	Assessments will be made according to the schedule listed below.
353	
354	

Registry Schedule of Assessments

	Baseline	3 months	6 months	12 months
DEMOGRAPHICS				
Age, ethnicity, gender	X			
Height (cm)	X			
Weight (kg)	X	X	X	X
Marital status	X			X
Education level	X			X
Employment status	X			X
Diagnosis of SMI	X			X
PRIMARY OUTCOME				
Weight loss	X	X	X	X
ANTHROPOMETIC MEA	SURES			
BMI (kg/m²)	X	X	X	X
Central Obesity (cm)	X	X	X	X
PATIENT REPORTED QU	J ESTIONNAIR I	ES		
SF12	X		X	X
PAM	X		X	X
Smoking status	X		X	X
COSTS				
Cost questionnaire	X		X	X
CLINICAL MEASUREME	ENTS			
HDL Cholesterol (mmol/l)	X			X
LDL Cholesterol (mmol/l)	X			X
Total Cholesterol (mmol/l)	X			X
Triglyceride (mmol/l)	X			X
Glucose metabolism (mmol/l)	X			x
Systolic BP (mm/hg)	X		X	X
Diastolic BP (mm/hg)	X		X	X
OTHER				
Intervention appointments not attended		Weekly	monthly	
Prescribed medication	X		X	X
Admission Mental health ward	x		X	x

356 357

STATISTICAL ANALYSIS

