394 analyses will be performed to assess the robustness of the results using different assumptions 395 regarding costs and effects. For the measurement and valuation of the costs the Dutch costing 396 guidelines will be used [30]. 397 398 Costs analysis 399 Costs will be measured using questionnaires based on the TiC-P [29] adapted to SMI patients group at 400 baseline, 6 and 12 months of follow-up. Cost data include costs of the intervention, other health care 401 utilization, patient and family costs, costs of productivity losses and costs for performing sports. 402 Quality adjusted life years will be calculated using the EQ-5D-5L [31] with Dutch reference values. 403 Uncertainty around incremental cost-effectiveness and cost-utility ratios will be estimated using 404 bootstrapping techniques and graphically presented on cost-effectiveness and cost-utility planes. 405 Bootstrapping will be used to estimate 95% confidence intervals around cost-difference per group. 406 407 Patient outcome analysis 408 The following effect measures will be included in the in the economic evaluation: 409 1) decrease in weight (kg); 410 2) improvement of cardiovascular risks (central obesity, lipids, blood pressure, glucose); 411 3) quality-adjusted life-years based on the Dutch tariff for the EQ-5D-5L 412 413 Cost-effectiveness and cost-utility analysis 414 The analysis will be done according to the intention-to treat principle. Missing cost and effect data will 415 be imputed using multiple imputation according to the MICE algorithm developed by van Buuren 416 [32]. Rubin's rules will be used to pool the results from the different multiple imputed datasets. 417 Incremental cost-effectiveness ratios (ICERs) will be calculated by dividing the difference in the mean 418 total costs between the treatment groups by the difference in mean effect between the treatment 419 groups. Bias-corrected and accelerated bootstrapping with 5000 replications will be used to estimate 420 statistical uncertainty surrounding the ICERs. Uncertainty surrounding ICERs will be graphically 421 presented on cost-effectiveness planes. Cost-effectiveness acceptability curves will also be estimated 422 using the net benefit framework [33]. Cost-effectiveness acceptability curves show the probability that 423 the tailored lifestyle intervention is cost-effective in comparison with usual care for a range of 424 different ceiling ratios thereby showing decision uncertainty [34]. 425 426 The effect of the lifestyle intervention on long-term cardiovascular morbidity risk and costs as 427 compared to usual care will be extrapolated over a time horizon of 10 years using a Markov model, if the study results indicate the intervention is effective. Health states that will be included in the model 428 429 are BMI\u27, BMI\u27, and death. Retention rates of the intervention will be based on the literature. 430 Cardiovascular risk and costs for each health states, and transitions between health states will be

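### The economic evaluation is specified as unadjusted mean differences, with no provision for FACT-team clustering, baseline utility or baseline costs

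*Protocol*

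**What the plan says.** **Design.** Under Justification study design: "Randomization will be performed at the level of the FACT teams". Under Randomisation: "Before persons with SMI are recruited, participating FACT-teams will be randomly allocated to serve" as intervention or control teams, after which the teams are told the result. Section 1.1 (Recruitment and consent) has team staff select and approach patients. Control patients receive a different letter that leaves out the lifestyle intervention.

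**Clinical analysis.** The sample size allows for clustering: "Assuming an ICC of 0.01 for clustering of persons with SMI within a" FACT-team. The data-analysis section uses mixed models with levels, corrects for significant baseline differences, and adds gender, age and variables that affect weight.

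**Economic analysis.** The General considerations introduce this as separate from the statistical analysis. The cost-effectiveness and cost-utility section then fixes:
- the estimator: "Incremental cost-effectiveness ratios (ICERs) will be calculated by dividing the difference in the mean" total costs by the difference in mean effect;
- missing data: these will "be imputed using multiple imputation according to the MICE algorithm" and pooled by Rubin's rules;
- uncertainty: "Bias-corrected and accelerated bootstrapping with 5000 replications will be used to estimate" it around the ICERs, followed by cost-effectiveness planes and acceptability curves.

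It names no team level, no resampling unit, no contents for the imputation model, and no covariate role for baseline utility or baseline costs. QALYs come from linear interpolation between measurements (Quality of life). Costs are collected at baseline, 6 and 12 months (Costs questionnaire).

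**The concern.** Cost-effectiveness is the question in the trial's title, yet this part of the plan takes no account of two features of the design that the clinical part does address.

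First, teams are the randomised unit. Costs and care use may be more alike within a team than between teams. An analysis that treats patients as independent would then give planes, intervals and acceptability curves that look more certain than they are. The curves are read as decision probabilities, and the trial's resource-use rates also feed the ten-year budget impact analysis.

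Second, the arms may differ at baseline. Unblinded staff recruit after allocation with arm-specific letters, so differences can be systematic as well as due to chance. An interpolated QALY contains the baseline utility, so a baseline difference passes directly into the incremental QALY. Baseline costs are likely to predict later costs but have no role in the estimator.

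There is also an inconsistency. Weight is estimated by a corrected mixed model in one section and enters an ICER denominator as a difference in means in another, so the trial could report two different weight effects.

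**Working it through.** **The plan's own figure.** The protocol gives no numerical target for the economic evaluation. Its sample size (4 kg, SD 10, alpha 0.05, power 0.80) reproduces with a two-sided test at 99 per group against the stated 100. Clustering is therefore acknowledged at design with ICC 0.01, for weight only.

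**Step 1: how baseline utility enters the QALY.** Linear interpolation over one year gives:
- utilities at 0, 6 and 12 months: QALY = 0.25·u0 + 0.50·u6 + 0.25·u12;
- utilities at 0 and 12 months: QALY = 0.50·u0 + 0.50·u12.

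Both are shown because the assessment schedule does not list the EQ-5D-5L separately. Take a baseline difference of 0.03 (an assumption, for illustration):
- through u0 alone: 0.25 × 0.03 = 0.0075, or 0.50 × 0.03 = 0.015;
- if the difference persists in full at every measurement: 0.03.

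**Step 2: cost of ignoring teams, if patients are resampled as independent.** Inputs are 224 patients and 21 teams (list of changes at the front of the protocol). Imputation keeps all patients, so m = 224/21 = 10.67. The design effect is DE = 1 + (m − 1)·ICC. The naive SE is too small by 1 − 1/√DE, and the coverage of a nominal 95% interval is 2Φ(1.96/√DE) − 1.

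| ICC | DE | √DE | SE too small by | Coverage |
|---|---|---|---|---|
| 0.01 (protocol, weight) | 1.097 | 1.047 | 4.5% | 93.9% |
| 0.02 (assumed) | 1.193 | 1.092 | 8.5% | 92.7% |
| 0.05 (assumed) | 1.483 | 1.218 | 17.9% | 89.2% |
| 0.10 (assumed) | 1.967 | 1.402 | 28.7% | 83.8% |

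Sensitivity to team size:
- with 20% dropout and no imputation, m = 224 × 0.8/21 = 8.53, giving 3.6% (ICC 0.01) and 14.8% (ICC 0.05);
- with the planned 260 patients in 18 teams, m = 14.44, giving 6.1% and 22.7%.

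**Step 3: which bootstrap would repair it.** A simulation with 11 + 10 teams of 11 patients, a normal outcome and percentile intervals (2000 trials, 400 resamples) gave:
- resampling patients: coverage 93.0%, 88.4% and 81.6% at ICC 0.01, 0.05 and 0.10;
- resampling whole teams: coverage about 91% to 92% at every ICC, because there are few teams;
- resampling teams and then patients within teams, uncorrected (further runs with the same layout): SE roughly 30% too large at ICC 0.01 and 20% to 25% too large at ICC 0.05, because within-team variance is counted twice.

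Neither uncorrected cluster bootstrap is adequate with 21 teams.

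**The case against.** The strongest reply is that the protocol is silent on these points rather than wrong. It does not state the resampling unit or the contents of the imputation model, and an analysis plan not at hand could supply both. That stands. A reader might infer that patients will be resampled as independent and that single-level MICE will be used, but the text says neither. Step 2 is therefore conditional.

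It can also be said that the clinical section covers the gap. It promises covariates in every analysis and treats secondary outcomes, which include the EQ-5D-5L, like the primary one. A difference in means could also be read as a difference in model-adjusted means. This does not settle the matter. The covariates named are gender, age and weight-related variables, and baseline correction depends on a significant difference. The economic section is set apart and states its own estimator without adjustment.

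A reader might further infer that the incremental QALYs and costs will be biased. The documents do not show that. Assume a utility SD of 0.25, 112 patients per arm and a design effect of 1.1. The SE of the baseline difference is then 0.25 × √(2/112 × 1.1) = 0.035, and a difference of at least 0.03 arises by chance about 39% of the time (28% to 48% for SD 0.20 to 0.30). That is sampling variation, which an unadjusted interval already reflects. It costs precision and is not bias. Bias needs systematic imbalance, which the recruitment procedure makes possible but which cannot be quantified here.

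Nor are the baselines wholly unused, since baseline utility is part of the QALY. What is missing is its role as a covariate.

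**Conclusion.** The point holds in a limited form. The protocol defines the ICER from differences in means with no stated adjustment, and describes imputation and bootstrapping without provision for teams, baseline utility or baseline costs. This sits in a team-randomised trial with unblinded recruitment after allocation, whose clinical analysis does provide for clustering and baseline differences. The section is detailed enough to name the imputation algorithm, pooling rule, bootstrap type and number of replications, so the estimator is specified and not merely deferred.

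The clustering effect is modest at the only ICC in the document and material only if costs or utilities cluster more strongly, for which no ICC is given. The calculation assumes equal team sizes and ignores stratification by centre, which may remove some between-team variance. The baseline effect depends on the size and persistence of any imbalance. It should be corrected before analysis, but it does not show that the economic results will be wrong.

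**What to change.** Specify in the analysis plan:

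- **Estimation.** Model incremental costs and effects jointly with a FACT-team level. Adjust costs for baseline costs, QALYs for baseline EQ-5D-5L utility, weight for baseline weight, and all of them for centre. Make these adjustments in advance, not conditional on a significant baseline difference.
- **Imputation.** Include arm and FACT team in the imputation model.
- **Uncertainty.** Derive the plane and acceptability curves from the joint model, or from a cluster bootstrap with a small-sample or shrinkage correction. State the resampling unit.
- **ICER.** Calculate it from these adjusted estimates.

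The cost is more programming and somewhat wider uncertainty from the team level. No new data are needed, since baseline measurements are already planned and study numbers carry the team code.

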1.1 Recruitment and consent

Patients from the involved FACT-teams will be evaluated for suitability by Clinical Nurse Specialists, treating physicians and other healthcare staff from the according teams. The teams will select patients on BMI information and other inclusion/exclusion criteria found in electronic patient files. FACTteam members will ask if suitable patients are interested in joining the study and give permission to share their private (contact) information with the research team. The research team will telephone potential participants who gave persmission and ask to send information letters and informed consent formsIf needed the research team can inform patients by telephone contact. The study will make use of one information letter/informed consent for the FACT-team patients allocated in the intervention condition, and a different information letter/informed consent for FACT-team patients allocated in the control condition. In the information letter for patients in the control condition the information regarding the lifestyle intervention is left out. In the control group patients will only be asked if they are willing to perform measurements for a small reimbursement. Trained health care workers from the FACT teams and treating physicians or other can provide and discuss information with the patients and can answer any open questions if needed. Patients can always contact the researchers for more information as well, and will be provided with contact information of the research team in the information letter. Apart from that, patients will be able to contact an independent researcher for questions.

495 496

497

498

499

500

501

502

Patients can take up to five workdays to sign the informed consent. If patients are prepared to participate, informed consent procedure is followed, where the patient signs two informed consent forms or receives a copy. The patient information letter and informed consent form will be attached as a separate document. The informed consent will be obtained from each patient before the baseline assessment of the study begins. Patients can bring the informed consent form at their first baseline measurement. Assessors of the baseline measurements can supply additional information of the study if needed.

504

505

506

507

508

509

510

511

512

513

514

515

516

517

518

519

520

521

522

Benefits and risks assessment, group relatedness

Participants in the lifestyle intervention condition directly benefit from participating in the study by receiving guidance and information on food and food-related behaviours, physical activity and smoking cessation that might have an positive impact on eating habits, other lifestyle behaviours and well-being. As a result patients can lose weight on short term and might reduce cardiovascular risks. Risks associated with participation in this study are deemed minor. Possible extra risk associated with the intervention includes injury as a result of indoor or outdoor physical activity. However, as the primary physical activity is walking outdoors, this is considered a minor risk. Apart from that risks evolving venepuncture (such as minor bruising, hematoma, bleeding complications, fainting or infections) could occur. However patients involved in the study have annual laboratory check-ups. The laboratory assessments are measured at baseline and after 12 months, this study will make use of the patient's annual check-ups whenever possible in order to avoid extra visits to the laboratory. The intervention itself can be challenging/exhausting for the participants, as it involves weekly group sessions of 2 hours in the first half year. However patients are clearly informed that they can stop with the study any time. Apart from that, healthcare staff from the FACT-teams can indicate if the burden becomes to high for a participant and advice the participant to stop the intervention. It is possible for nurses to assess this in the group sessions. We think these risks are in proportion to the potential value of this study, which is looking at several lifestyle behaviours that might be effective in the prevention of cardiovascular disease in the SMI population. This could potentially be really important for mental health care in the future.

523524525

526

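### Teams learn their allocation before their own unblinded staff select and first approach patients, with letters that differ by arm, so identification and consent bias of unknown direction and size is possible

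*Protocol*

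**What the plan says.** All references are to the Protocol; no SAP is at hand.

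- **Order.** Randomisation, blinding and treatment allocation: "Before persons with SMI are recruited, participating FACT-teams will be randomly allocated to serve" as intervention or control teams. Study design gives the same order.
- **Disclosure.** Same section: "The randomization results will be communicated to the participating" teams, by the researchers. No delay until patients have been identified is mentioned.
- **Blinding.** Same section: "Blinding of patients and FACT-team members is not possible due to the nature of the intervention".
- **Who judges and selects.** Section 1.1, Recruitment and consent, gives both tasks to the teams themselves: "Patients from the involved FACT-teams will be evaluated for suitability by Clinical Nurse Specialists, treating physicians and other healthcare staff from the according teams". On how the selection is made, it adds: "The teams will select patients on BMI information and other inclusion/exclusion criteria found in electronic patient files".
- **Who makes the first approach.** Section 1.1: FACT-team "members will ask if suitable patients are interested in joining the study". The research team telephones only those who have given permission.
- **What patients are told.** Section 1.1 provides a separate letter and consent form for each arm. "In the information letter for patients in the control condition the information regarding the lifestyle intervention is left out", and "In the control group patients will only be asked if they are willing to perform measurements for a small reimbursement".
- **Criteria needing judgement.** Under Exclusion criteria, the treating physician or psychiatrist assesses contra-indications. Cognitive impairment is an exclusion when it is severe enough to interfere with consent, questionnaires or taking part in a group intervention.
- **Handling of imbalance.** Statistical analysis plans a descriptive baseline comparison as a check on the randomisation. It adjusts for baseline differences that are significant, and for age, gender and further, unnamed predictors of weight.

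**The concern.** In a cluster trial, randomisation balances the teams in expectation. It balances the patients only if the way they enter does not depend on allocation. Here entry comes after allocation, and allocation can affect it in two ways.

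1. **Identification.** Staff who know their arm decide who is suitable and whom to ask.
2. **Consent.** Patients in one arm decide about a year-long lifestyle programme. Patients in the other decide about being measured, without being told of the programme.

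If either route selects on something that predicts weight change, the primary 12-month contrast mixes the programme's effect with a difference between the people enrolled. The intention-to-treat principle does not help, because it starts from those enrolled. The same contrast feeds the cost-effectiveness ratios and, if the intervention appears effective, the ten-year Markov model.

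**Working it through.** No figure in the Protocol is in dispute, so the check follows the recruitment path in order and asks at each step whether allocation is known and whether discretion exists.

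1. **Teams are randomised.** No patients have been recruited. Stratification by centre makes the arms comparable as sets of teams. It does not act on which patients are later chosen.
2. **Result communicated.** The date on which each team learns its arm is not given. That it precedes selection is inferred from the stated order, the unblinded staff and the arm-specific letters. Nothing in the text points the other way.
3. **File screen by team staff.** BMI and age are objective. Contra-indications and the degree of cognitive impairment need judgement. The criteria are worded identically for both arms, but they are applied by people who know the arm.
4. **First approach by team staff.** No rule covers the order of approach, and there is no requirement to approach everyone eligible. The research team's telephone call comes after this filter and cannot undo it.
5. **Information and consent.** Content differs by arm as documented. The oral approach in step 4 is not described separately by arm, so the documented difference lies in the letter, the form and what is asked.
6. **Baseline comparison.** Patients enter after randomisation, so an observed imbalance may be chance or selection, and the comparison cannot tell which. An absence of imbalance on measured variables says nothing about unmeasured ones.
7. **Adjustment.** Willingness to change is not measured as such. The PAM-13 is scheduled at baseline and covers knowledge, skills and confidence in health-related self-efficacy, so it is a partial proxy. It is not named as a covariate, and it would enter under the significance rule only if the arms happened to differ significantly on it.

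**Can the size be worked out?** For a single unmeasured trait, the spurious arm difference is

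bias = (p_I − p_C) × d,

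where p_I and p_C are the shares of enrolled patients with the trait in each arm, and d is the difference in 12-month weight change between patients with and without it. The Protocol gives none of the three. The sign depends on p_I − p_C, which is equally unknown. No figure in kilograms, and no fraction of the 4 kg target difference, can therefore be derived.

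**Room for choice.** With 224 patients from 21 teams, enrolment averages 224 / 21 = 10.7 per team. The number of eligible patients per team is not stated, so how selective this was cannot be judged either.

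**The case against.** The best defence is that selection follows one written set of criteria applied to electronic files, that randomising teams was needed to avoid contamination, and that the analysis adjusts for baseline differences. Part of this stands. The criteria are common to both arms, and contamination is a sound reason for clusters. But it is a reason to randomise teams, not to have staff who know the allocation do the recruiting, and common wording does not make a judgement blind.

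Several stronger readings are tempting, and the Protocol does not support them.

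- **That intervention teams look for motivated patients and control teams do not.** No arm-specific search rule is written anywhere.
- **That the bias favours the intervention.** Staff might equally offer programme places to their heaviest or hardest-to-treat patients. The text does not settle it.
- **That anyone unable to join a group is excluded, and that this works differently by arm.** The exclusion is limited to cognitive impairment, and its wording is the same for both arms.
- **That payment is an inducement for controls only.** Section 1.2, Incentives, pays study participants for measurements without distinguishing arms. The real contrast is whether the programme is mentioned.
- **That adjustment is powerless.** The PAM-13 could recover part of a motivational difference if it were used. What can be said is that adjustment cannot be relied on to remove the bias.

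It is also fair to object that, with 224 patients already included, reordering recruitment comes too late for them. That stands, and it makes the retrospective comparison the live step for this trial.

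**Conclusion.** The point holds as a weakness of design: followed exactly, the plan allows selection after randomisation, by staff and by patients' consent, to enter the primary contrast, and no stated safeguard closes either route. It rests on one inference, that teams know their arm when they select patients, which the stated sequence makes the natural reading. Direction and size are unknown, and the Protocol contains no evidence that the arms actually differ. The change is worth making because it is cheap and closes one of the two routes. The finding does not by itself show that the trial's result is wrong.

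**What to change.** **Protocol wording, in Randomisation, blinding and treatment allocation and in section 1.1.** Require each team to complete its file-based eligibility screen under identical criteria, and to lock a dated, coded list of eligible patients, before its allocation is communicated. Because randomisation is stratified by centre, release a centre's results only when all its teams have locked their lists, since one team's arm may reveal another's. Afterwards, approach patients only from the list. Record and report, by arm, how many were listed, approached, refused and consented.

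**What this does and does not cure.** It removes identification by staff who know the allocation. It does not remove differential consent arising from the different letters. The counts make that visible, and it should be stated as a limitation.

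**Teams already recruited.** Compare enrolled with file-eligible patients by arm, on variables held in the files. Section 1.1 seeks patients' permission before contact details reach the research team, so use de-identified or aggregate data, and only where privacy rules allow. Describe the baseline comparison as unable to separate chance from selection.

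**Cost.** A short delay before allocation is released, a list that ages somewhat before patients are approached, and a simple log. The screening is work the teams already do. The retrospective comparison takes additional effort and may not be feasible everywhere.
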